4.4.1 Screening

Patients planned for a diagnostic bronchoscopy procedure under general anaesthesia at the investigational site will be evaluated by the anaesthesiologist to determine if AuraOnce can be clinically justified for the procedure. If AuraOnce can be clinically justified and the subject fulfils the inclusion criteria for the study, he/she will be enrolled in the study. If AuraOnce cannot be clinically justified or if the patient does not fulfil the inclusion criteria, he/she will be excluded from the investigation and receive the standard treatment off this investigation.

4.4.2 Randomisation

Not applicable

4.4.3 Investigational procedures

4.4.4 Pre-examination of the airway

- Before inserting the AuraOnce a pre-examination will be performed to ensure that the anatomy is applicable for laryngeal mask placement.
- An examination of the airway will be performed and include the following measures:
 - o Airway cleaned (yes/no)
 - o Inter-incisor distance (normal/reduced)
 - o Significant overbite (no/yes)
 - o Mandibular space (normal/reduced)
 - o Cervical motion (normal/restricted)
 - o Short thick neck (no/yes)

4.4.5 Preparation for use

- The device will be prepared, and size will be chosen according to users' standard clinical procedure.

4.4.6 Insertion of AuraOnce

- All participants are experienced in placement of laryngeal masks and placement will be performed according to standard clinical practice.
- Number of attempts for correct placement will be noted in the CRF
- After insertion the following information is noted in the CRF:
 - o Leakage (yes/no) – if yes: signs of leakage are noted
- After insertion the user perception of the AuraOnce placement is obtained regarding:
 - o Ease of insertion
 - o Ease of obtaining seal

Protocol – Non-interventional study

8/13

Project/Product Name: AuraOnce performance observation
Study ID: CIS-016

[figure not shown]
07-OCT-2019

- Overall performance of the product

4.4.7 Bronchoscopy procedure

Prior to the bronchoscopy procedure, which the patient is scheduled for, an assessment of the AuraOnce will be performed.

- The head of the patient is placed in neutral position.
- A lubricated flexible video bronchoscope is inserted through the AuraOnce.
- A picture is taken of the vocal cords to assess the placement of AuraOnce
 - The picture is kept with the CRF
- The percentage of glottic opening (POGO), defined on a scale from 0-100 (see figure below) is used to confirm correct placement (6). The percentage of opening seen indicates whether AuraOnce is able to adapt to the anatomy.

- A picture of the AuraOnce cuff is taken, specially focussing on the tip
 - The picture is printed and kept with the CRF
 - If any issues with the cuff is observed (especially folding) it must be described in the CRF.

After assessing the AuraOnce the diagnostic flexible bronchoscopy procedure is performed as planned and the AuraOnce is removed after the procedure. The bronchoscopic procedure and removal of AuraOnce is not part of this investigation, and the study ends as the bronchoscope passes the vocal cords.

4.4.8 Follow-up procedures

Not applicable

4.4.9 Missed follow-up

Not applicable as no follow up is done

4.4.10 Lost to follow-up

Not applicable as no follow up is done

4.4.11 Procedures performed by sponsor representatives

Not applicable

4.4.12 Subject Identification and Confidentiality

Each subject will be given a subject number, however all data collected will be anonymized and it will not be possible to identify the subject after completion of the procedure. No patient registration list will be created to ensure patient confidentiality.

Data entered on the CRF are confidential and will only be available to the sponsor (including sponsor delegates), members of data management teams, the statistician, data monitoring

Protocol – Non-interventional study

9/13

Project/Product Name: AuraOnce performance observation
Study ID: CIS-016

07-OCT-2019

board members or clinical event committee members if involved, and if requested to regulatory authorities.

4.5 Monitoring plan

The sponsor is responsible for ensuring appropriate monitoring of the clinical investigation activities.

During the period of the investigation a representative of the sponsor, [name], [contact] or [name], [contact], will act as monitor/s of the investigation. The investigator may contact [name] or [name] at any time. The monitor will be the primary contact for the principal investigator and clinical investigation site personnel.

Monitoring activities are mandatory as per good clinical practice, however the extend and depth of these activities depend on the criticality of the clinical investigation, speed of enrolment, the experience of the clinical investigation site personnel in carrying out clinical investigations and specific study designs.

For the purpose of this clinical investigation the below described monitoring procedures have been determined.

4.5.1 Monitoring visits

The monitor/s is responsible for planning the monitoring visit including initiation visit, routine visit and close-out visit.

4.5.2 Initiation visit:

The initiation visit will be performed before the study is initiated. The aim of this meeting is to train the investigator(s) on the investigation procedure, perform a page-by-page revision of the CIP with emphasis on reporting of deviations, adverse events and how to complete the CRF. Moreover, contract signature and written EC opinion will be verified, and monitoring arrangements will be discussed. It is required that all investigators participating are present in this meeting.

4.5.3 Routine Visit

Monitoring of the CRFs will be performed after the first day of data collection (4-7 subjects are expected to be completed at this point). Ongoing monitoring will be performed by the observer who will be presented during all data collections. The aim of these routine visits is to corroborate the clinical investigation progress. CRF will be monitored for completeness and correctness of the data. It is required that at least one investigator is available during monitoring visits.

4.5.4 Close-out visit:

The close-out visit will be performed when the data collection has been completed. The aim of this meeting is to close financial aspects, check that all essential documents are complete and up to date, all outstanding queries are resolved, current state of all adverse events is documented, arrangement for achieving all clinical investigation documentation, device accountability and collection of the original CFR.

Protocol – Non-interventional study

10/13

Project/Product Name: AuraOnce performance observation
Study ID: CIS-016

07-OCT-2019

4.5.5 Source data verification

No source data verification will be performed for this study, as there will be no access to the patient file. Name, address/contact information and personal identification number (CPR) will not be collected for this study. To ensure correct data collection and high-quality data, an observer dedicated for the study will be available during the entire data collection to double check that all data is noted correct. It will be the same observer during the entire data collection.

5. AUDIT

Audit of the clinical investigation may be conducted by the sponsor or third parties designated by the sponsor to evaluate compliance with the CIP, written procedures and international standards (2). These audits may cover all involved parties, systems and facilities and are independent from routine monitoring. The aims of the audit are:

- to assess the effectiveness of the monitoring,
- whenever there are repetitive deviations from the CIP,
- to prepare the investigation for a regulatory inspection,
- when requested by a regulatory authority, etc.

Audits may be performed during the investigation. All parties will be informed in advance of the date and objective of the audit.

6. STATISTICAL CONSIDERATIONS

6.1 Sample size

No sample size calculations have been performed for this study as the data obtained only will form basis for quality control of the performance of the Ambu AuraOnce disposable Laryngeal Mask.

The study will include a minimum of 15 and a maximum of 20 adult patients already scheduled for a diagnostic flexible bronchoscopy procedure in general anesthesia using a laryngeal mask.

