4. DESIGN OF THE CLINICAL INVESTIGATION

4.1 General

This study is designed as a single-center, prospective observational, non-controlled, non-interventional study with an investigation period lasting for one day (during one bronchoscopy procedure). The study will take place in Denmark.

The study will include minimum 15 adult patients planned for a diagnostic flexible bronchoscopy procedure in general anaesthesia using a laryngeal mask.

The involved site will include subjects during a one month period, October 2019. However, the study will not be initiated before the study protocol is duly approved, i.e. by site, Ambu and Ethics Committee if relevant (if EC approval is not needed a written opinion from the EC must be obtained). If the number of subjects cannot be included in time, the sponsor will decide whether the study period should be extended, or the study should be closed.

The intention is to perform a quality assessment of the AuraOnce. Subjects will not be asked to participate in this study as it is a quality study (see section 16) where the AuraOnce is used within its intended use and according to normal clinical procedure.

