4.3 Subjects

The clinical investigation will be conducted on minimum 15 subjects and maximum 20 subjects enrolled in one clinical investigation site.

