4.3.3 Subject withdrawal or discontinuation

Patients not completing the clinical procedure as intended by the investigator are considered as drop-outs as the evaluation form will lack information of the device. In case of drop-outs the study will not be completed until the minimum number of subjects is included.

Subjects will be withdrawn from the clinical investigation for the following reason:

- a. Withdrawal by investigator for e.g. safety reasons

The reason for withdrawal will be investigated and carefully documented in the appropriate section of the case report form (CRF).

If a subject is replaced the new subject is given a new subject number.

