4.3.5 Duration of the clinical investigation

The data collection is expected to last three days within a two months period. The subjects are included in the study when the investigator has ensured that they fulfill the in- and exclusion criteria and they are completed when the bronchoscopist have confirmed the laryngeal mask placement (by taking a picture) and starts the planned bronchoscopy procedure. The expected duration of each subject's participation is estimated to be less than one hour.

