6.2 Pass/fail criteria

In 90% of the cases the AuraOnce must be correctly centred above vocal cords with no clinical significant air leak and using maximum 3 placement attempts.

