6.3.2 Handling of dropouts and missing data

Patients not completing the clinical procedure as intended by the investigator are considered as drop-outs as the evaluation form will lack information of the device. Drop-outs are

Protocol – Non-interventional study

11/13

Project/Product Name: AuraOnce performance observation
Study ID: CIS-016

07-OCT-2019

compensated in the sample size estimation to ensure that a complete data set is collected for minimum 15 patients. Missing data will not be imputed.

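### The denominator of the only pass/fail rule can shift with results: a failed placement may be replaced as a drop-out, and the final n is open between 15 and 20

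*Combined protocol and SAP*

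**What the plan says.** **The rule.** Section 6.2, repeated in section 3, sets the criterion: "In 90% of the cases the AuraOnce must be correctly centred above vocal cords", without a clinically significant leak and within three attempts. It is a percentage. No count is given, and no n at which it is judged.

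**The number of subjects.** Section 6.1 states: "The study will include a minimum of 15 and a maximum of 20 adult patients". Section 4.3 gives the same range, and section 4.1 gives only the minimum. Section 6.1 also says that no sample size calculation was made.

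**Drop-outs.** Section 4.3.3 states: "Patients not completing the clinical procedure as intended by the investigator are considered as drop-outs". Its reason is that their form will lack information on the device. The study stays open until the minimum is reached, and a replacement gets a new number. Section 6.3.2 repeats the definition and says that drop-outs are "compensated in the sample size estimation to ensure that a complete data set is collected for minimum 15 patients". Section 4.3.5 regards a subject as complete once the bronchoscopist has confirmed the mask's placement by a picture and begins the planned procedure.

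**Timing.** Section 4.3.5: "The data collection is expected to last three days within a two months period". Section 4.5.3, on the first collection day: "4-7 subjects are expected to be completed at this point". Section 4.1 gives a one-month window. If the number is not reached in time, "the sponsor will decide whether the study period should be extended, or the study should be closed".

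**The concern.** A pass/fail proportion is only as firm as its denominator, and here two things can move it.

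(a) The cases most likely not to go as intended include those in which the mask could not be seated or sealed. These are the failures that the criterion is meant to count. If they are classed as drop-outs and replaced, the reported proportion is biased upward.

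(b) The final n is free within a range over which the number of permitted failures changes, and whoever decides whether to enrol another subject can know the running count. Leakage and attempts are recorded at insertion (section 4.4.6), CRFs are checked after the first day (section 4.5.3), and one observer attends every collection (section 4.5.5).

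What is at stake is the credibility of the pass or fail verdict. The individual data are not affected.

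**Working it through.** The plan gives no sample size calculation, power or drop-out rate, so there is no figure to reproduce. The inputs are the 90% mark (section 6.2), the range 15 to 20 (sections 4.3 and 6.1) and the drop-out text (sections 4.3.3, 4.3.5 and 6.3.2). True success rates are assumptions, because the documents give none.

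**Part (a): can a failed placement leave the denominator?**

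- If the mask cannot be seated or sealed, the procedure has not gone as intended, which meets the drop-out definition in section 4.3.3.
- Placement has not been confirmed by a picture, so the subject is not complete under section 4.3.5.
- The assessment through the mask (section 4.4.7) may be missing, so the subject may not count towards the 15 complete data sets of section 6.3.2.
- Nothing in section 6.2 or 6.3 brings such a subject back as a failure.

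The effect, with 15 complete cases reported:

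| Failed placements replaced | Reported | All enrolled subjects counted |
|---|---|---|
| 1 | 14/15 = 93.3%, pass | 14/16 = 87.5%, fail |
| 2 | 15/15 = 100%, pass | 15/17 = 88.2%, fail |
| 5 (limit set by the cap of 20) | 15/15 = 100%, pass | 15/20 = 75.0%, fail |

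The last row is a bound, not a forecast. With one replaced failure and no other, 15/15 and 15/16 (93.8%) both pass.

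**Part (b): does the verdict depend on n?**

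Read as at least 90%, required successes = 0.9n rounded up.

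| n | 15 | 16 | 17 | 18 | 19 | 20 |
|---|---|---|---|---|---|---|
| Required | 14 | 15 | 16 | 17 | 18 | 18 |
| Failures allowed | 1 | 1 | 1 | 1 | 1 | 2 |
| Effective mark | 93.3% | 93.8% | 94.1% | 94.4% | 94.7% | 90.0% |
| Rate with two failures | 86.7% | 87.5% | 88.2% | 88.9% | 89.5% | 90.0% |

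With no failure or one, every n passes. With three, every n fails (at best 17/20 = 85.0%). Only with exactly two failures does n decide: 17/19 fails and 18/20 passes.

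The timing text does not settle n. If all three days resembled the first (an assumption), 3 × 4 = 12 to 3 × 7 = 21 subjects would result, which covers the whole range.

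**Size of (b) if n were chosen freely.** A pass at any n from 15 to 19 requires at most one failure in the first 15. A pass at some n is therefore either at most one failure in 15, or two failures in 15 followed by five successes:

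P(pass at some n) = P(at most 1 failure in 15) + P(2 failures in 15) × p⁵

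At p = 0.90: 0.5490 + 0.2669 × 0.5905 = 0.5490 + 0.1576 = 0.7066.

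| Assumed true rate | Fixed n=15 | Fixed n=20 | Free choice | Gain over n=20 |
|---|---|---|---|---|
| 80% | 16.7% | 20.6% | 24.3% | 3.7 points |
| 85% | 31.9% | 40.5% | 44.5% | 4.0 points |
| 90% | 54.9% | 67.7% | 70.7% | 3.0 points |
| 95% | 82.9% | 92.5% | 93.3% | 0.9 points |

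Over fixed n=15 the gain is larger (15.8 points at 90%), but much of that is simply the lower effective mark at n=20.

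**The case against.** The strongest reply is that this is a descriptive quality study with no hypothesis. A proportion of completed cases is defined at any n and needs no preset count. The 15 to 20 range is most likely a drop-out allowance. The verdict depends on n at only one failure count, and a report that gives numerator and denominator shows its own basis. All of this stands. It is why the open n alone would be little more than a missing detail, and why no type I error is at issue.

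On part (a), the defence is that a CRF is required for every enrolled subject (sections 4.4 and 7.1) and records attempts and leakage, so a careful team could score a failed placement as a failure. That is possible, but the drop-out text permits the opposite, and no sentence decides between them.

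Three stronger readings are not supported:

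- A reader might infer that enrolment will stop when the results look good. No passage says so. Section 4.1 gives the sponsor a decision only for a shortfall, and patient flow may well set n.
- A reader might infer that the plan instructs that failed placements be discarded. It does not. Section 4.3.3 gives missing information as its reason; the gap is that failed placements are not carved out.
- A reader might take the chance that n=15 and n=20 give opposite verdicts in the same run as the size of the bias: 0.1576 + 0.0297 = 18.7% at an assumed 90%. That figure compares the two extremes and mostly reflects sampling variation and the lower mark at n=20.

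**Conclusion.** The point holds as a minor one. Part (a) carries the more weight: followed as written, the drop-out text can remove and replace a failure of the criterion, and a single such case can turn 87.5% into 93.3%. How often this would happen cannot be estimated from the documents. Part (b) is a narrower gap. It matters only with exactly two failures, and free choice of n would be worth about 1 to 4 points over fixed n=20. That rests on reading the mark as at least 90%, on independent cases, and on assumed true rates of 80% to 95%. Stopping on results remains hypothetical.

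**What to change.** Before the first subject:

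1. **Sections 4.3.3 and 6.3.2.** State for the analysis that an enrolled subject in whom AuraOnce insertion was attempted, but correct placement or seal was not achieved, counts as a failure in the 90% criterion and is not a replaceable drop-out.
2. **Section 6.1.** State an end of enrolment that does not depend on results: a fixed evaluable n or a fixed last collection day, at the sponsor's choice. A fixed day also needs reconciling with the floor of 15 and the cap of 20. With two failures the verdict would still vary with n, but n would no longer be open to choice with results in view.
3. **Section 6.2.** State that the criterion is judged once, on all evaluable subjects including the failures in item 1, with numerator and denominator reported. List the required counts: 14/15, 15/16, 16/17, 17/18, 18/19, 18/20.
4. **Section 6.3.2.** Replace the reference to a sample size estimation, since section 6.1 says none was made. Say instead that drop-outs are replaced within the cap until the minimum is reached.

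There is no need to prescribe 14/15 or to keep later subjects out of the verdict. The choice of n has its own price: at an assumed true rate of 95%, the device fails the criterion 17.1% of the time at n=15 and 7.5% at n=20.

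The cost is protocol wording, with no extra procedures and no increase in the cap. The downside for the sponsor is that the reported success rate may be slightly less favourable.

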6.2 Pass/fail criteria

In 90% of the cases the AuraOnce must be correctly centred above vocal cords with no clinical significant air leak and using maximum 3 placement attempts.

6.3 Statistical analyses

6.3.1 General aspects

Descriptive statistics of all measured outcomes are provided (median and range or mean and standard deviation as appropriate). The study is not sufficiently powered to explore patient characteristics related to unsuccessful placement of laryngeal mask.

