3. OBJECTIVES AND HYPOTHESES

The objective of this study is to observe the performance of the AuraOnce through clinical assessment and endoscopic imaging to ensure ongoing documentation on quality of the product in regards to correct placement remains high.

This is an observational study with no hypothesis. However, a success criterion is set saying that in 90% of the cases the AuraOnce must be correctly centred above vocal cords with no clinical significant air leak and using maximum three placement attempts.

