3.1 Primary

Primary endpoint¹:

- Leakage (yes/no), if yes insert signs of leakage

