3.2 Secondary

Secondary endpoints²:

- Questionnaire – interview to anaesthesiologist/nurse
 - o Ease of insertion (5-point scale, very difficult to very easy)
 - o Ease of obtaining seal (5-point scale, very difficult to very easy)
 - o Overall performance (5-point scale, very bad to excellent)
- Opening placed just above vocal cords (yes/no) correct positioning is documented by endoscopic picture (including POGO score)

¹ Primary endpoint(s) is (are) principal indicator(s) used for assessing the primary hypothesis of a clinical investigation. It is also used to calculate sample size.

² Secondary endpoints are indicators used for assessing the secondary hypotheses of a clinical investigation.

Protocol – Non-interventional study

5/13

Project/Product Name: AuraOnce performance observation
Study ID: CIS-016

07-OCT-2019

- Folding of tip (yes/no) - is documented by endoscopic picture

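### The denominator of the 90% pass/fail rate is not settled for failed placements: the drop-out rules, read literally, can remove and replace the failures that section 6.2 is meant to count

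*Combined protocol and SAP*

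**What the plan says.** The criterion appears twice. Section 3 says "a success criterion is set saying that in 90% of the cases the AuraOnce must be correctly centred above vocal cords", and section 6.2 repeats it: "In 90% of the cases the AuraOnce must be correctly centred above vocal cords with no clinical significant air leak". Both add a limit of three placement attempts. Neither says which subjects make up the cases.

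Three sections bear on who is counted:
- Section 4.3.5 includes a subject once the eligibility criteria are checked. The subject is completed when the bronchoscopist has confirmed mask placement with a picture and starts the bronchoscopy.
- Section 4.3.3: "Patients not completing the clinical procedure as intended by the investigator are considered as drop-outs". The reason given is that the evaluation form will lack device information. The study then stays open until the minimum number is reached, and a replacement subject gets a new number.
- Section 6.3.2 repeats the drop-out definition, aims at complete data for at least 15 patients, and adds: "Missing data will not be imputed".

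Section 4.3 sets the size at "minimum 15 subjects and maximum 20 subjects enrolled in one clinical investigation site". Section 4.4.6 has the number of attempts noted in the CRF.

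On summaries, section 6.3.1 offers: "Descriptive statistics of all measured outcomes are provided (median and range or mean and standard deviation as appropriate". The primary endpoint in 3.1 is "Leakage (yes/no), if yes insert signs of leakage". Position in 3.2 is "Opening placed just above vocal cords (yes/no"), and tip folding is also yes/no. Section 3 states that the study has no hypothesis, and 6.1 that no sample size was calculated.

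**The concern.** A subject whose mask cannot be placed fits two rules. Under 6.2 the subject has missed a component of success and is a failure. Under 4.3.5 the subject never reaches completion, so 4.3.3 and 6.3.2 allow the subject to be treated as a drop-out and replaced.

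The ambiguity falls on the event that the criterion exists to detect. If failed placements leave the denominator, the rate describes only subjects in whom placement was confirmed, and it can only move upward. With 15 to 20 subjects, one or two such cases can decide the verdict. If the rule is not fixed beforehand, it may be chosen once the results are known.

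A smaller matter goes with it. No section asks for counts with a denominator, or for an interval, for the yes/no outcomes or the composite. An interval would not repair a wrong denominator; it would be precise about the wrong quantity.

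**Working it through.** There is no sample size or precision figure in the plan to reproduce.

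**Inputs.** 90% threshold (3, 6.2); 15 to 20 subjects (4.3, 6.1); at least 15 complete data sets (6.3.2). **Assumptions.** A pass is an observed rate of at least 90%; the interval level is 95% two-sided (the plan sets none); the final n is treated as fixed.

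**Step 1, pass mark.** m = 0.9n rounded up. For n = 15, 16, 17, 18, 19, 20 this gives 14, 15, 16, 17, 18, 18. That is at most one failure for n = 15 to 19 and at most two for n = 20.

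**Step 2, one failed placement left out.** If m of n counted subjects succeed and one failed placement was dropped, the rate over all attempted insertions is m/(n + 1).

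**Step 3, precision.** The Clopper-Pearson lower limit for x/n is the p that solves P(X ≥ x | n, p) = 0.025. For x = n it is 0.025^(1/n); for example 0.025^(1/15) = 78.2% and 0.025^(1/20) = 83.2%.

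| n counted | Smallest pass | With one dropped failure restored | Lower limit, smallest pass | Lower limit, all successes |
|---|---|---|---|---|
| 15 | 14/15 = 93.3% | 14/16 = 87.5%, fail | 68.1% | 78.2% |
| 16 | 15/16 = 93.8% | 15/17 = 88.2%, fail | 69.8% | 79.4% |
| 17 | 16/17 = 94.1% | 16/18 = 88.9%, fail | 71.3% | 80.5% |
| 18 | 17/18 = 94.4% | 17/19 = 89.5%, fail | 72.7% | 81.5% |
| 19 | 18/19 = 94.7% | 18/20 = 90.0%, pass | 74.0% | 82.4% |
| 20 | 18/20 = 90.0% | not possible within 20 enrolled | 68.3% | 83.2% |

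**Step 4, perfect results.** 15/15 with one dropped failure restored is 15/16 = 93.8%, still a pass. With two it is 15/17 = 88.2%, a fail. 18/18 with two is 18/20 = 90.0%, still a pass.

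**Intervals for the restored rates.** 14/16: 61.7% to 98.4%. 15/17: 63.6% to 98.5%.

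**The case against.** The best defence is that the plan already leans towards counting a failed placement. Section 6.2 makes the attempt limit part of success. Attempts are recorded (4.4.6), a CRF is required for every enrolled subject (4.4, 7.1), and 6.3.1 speaks of unsuccessful placement as something that could have been explored. The stated reason for calling someone a drop-out is missing device information, and a failed placement does yield some. This shows that a sensible analyst could reach the right answer. It does not remove the completion rule in 4.3.5, which points the other way, so a clarifying rule is still needed.

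The second defence is that this is a descriptive quality study with no hypothesis. That stands. A reader might infer that the plan uses a pass to show a true rate of 90% or more; no section says so. The lower limits are therefore a caution about interpretation and do not show an error in the plan's reasoning.

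A reader might also infer that 6.3.1 prescribes unsuitable statistics for most outcomes. Of the six listed endpoints, three are yes/no and three are 5-point scales; POGO and attempts are numeric. Most analysts would report counts for the yes/no items without being told, and the composite percentage is implied by the criterion. Taken alone, that wording is a minor reporting gap.

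Last, a reader might infer that any dropped failure reverses the verdict. The table shows otherwise at n = 19, and one dropped failure leaves 15/15 a pass. The documents give no failure rate, so the examples show what can happen, not what is likely.

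**Conclusion.** The point holds for the denominator. Sections 6.2, 4.3.3, 4.3.5 and 6.3.2 leave a failed placement both a failure and a replaceable drop-out, and under the second reading the rate is biased upward. At the smallest pass for n = 15 to 18, one dropped failure turns a pass into a fail; two do the same to 15/15.

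This rests on reading 90% as an observed rate of at least 90%, and on a failed placement occurring at all. It does not establish that failures would in fact be dropped.

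On precision, no result with 15 to 20 subjects has an exact two-sided 95% lower limit above 83.2%. A pass is compatible with a true rate well below 90% and should be described as meeting an observed benchmark. This part is good reporting practice and does not correct a miscalculation.

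**What to change.** These are analysis definitions only; nothing changes in clinical management or sample size.

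1. **Section 6.2, cross-referenced from 4.3.3 and 6.3.2.** The denominator is all enrolled subjects in whom AuraOnce insertion was attempted. A subject not correctly placed within three attempts, or failing any other component, is a failure. That subject stays in the denominator even if another is enrolled to reach 15 complete data sets.
2. **Missing components.** Subjects with no failed component but a missing one are listed with the reason. The rate is shown both without them and with them counted as failures. This avoids an open-ended exclusion for stops judged unrelated to the device, and nothing is imputed in the data set.
3. **Section 6.3.1.** Report leakage, position, tip folding and the composite as n/N, percentage and exact (Clopper-Pearson) 95% interval.
4. **Sections 3 and 6.2, same wording.** A pass is an observed proportion of at least 90%, reported with its interval; it does not show a true rate of 90% or more.

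The cost is a few sentences and a small addition to the analysis code, with no extra subjects or data. The downside is a lower observed rate if failed placements occur, and a slightly less favourable stated conclusion.
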